6.3 Assignment of Global Unique Identifier (GUID)

The GUID is a computer-generated alphanumeric code that is unique to each research participant. It protects identifiable information allowing de-identified data to be integrated and tracked over time across multiple projects, databases, and biobanks.

6.4 Measures to Minimize Bias: Randomization and Blinding

Subjects will be randomized 1:1:1:1 into each of the 4 factorial-design groups: IMAGINE-PD/Virtual, IMAGINE-PD/Telephone, Virtual/Virtual, Virtual/Telephone. Participants and investigators will be blinded to the genetic testing results (research or clinic confirmation test) until the disclosure visit. The non-clinical researcher from the MIND study who will provide blinded lists of potential participants will not be involved in study conduct, data collection, patient interaction, or have access to any clinical data collected in the GET Virtual PD study.

6.5 Study Intervention Compliance

The CRCU will provide web-analytics demonstrating time spent one each page, total time spent on the website, number of clicks, and times visited to the site. This information will be used to infer compliance with observing the pre-test counseling via IMAGINE-PD.

7 STUDY INTERVENTION DISCONTINUATION AND PARTICIPANT DISCONTINUATION/WITHDRAWAL

7.1 Discontinuation of Study Intervention

Discontinuation from IMAGINE-PD or virtual/telephone genetic counseling does not mean discontinuation from the study, and remaining study procedures should be completed as indicated by the study protocol. If a clinically significant finding is identified (including, but not limited to changes from baseline) after enrollment, the investigator or qualified designee will determine if any change in participant management is needed. Any new clinically relevant finding will be reported as an adverse event (AE).

The data to be collected at the time of study intervention discontinuation will include the following:

• All planned subsequent study interventions

7.2 Participant Discontinuation/Withdrawal from the Study

Participants are free to withdraw from participation in the study at any time upon request.

An investigator may discontinue or withdraw a participant from the study for the following reasons:

• If any clinical adverse event (AE), or other medical condition or situation occurs such that continued participation in the study would not be in the best interest of the participant

The reason for participant discontinuation or withdrawal from the study will be recorded in the study log. Subjects who sign the informed consent form and are randomized but do not receive the counseling or clinical confirmation testing may be replaced. Subjects who sign the informed consent form and are randomized and receive the genetic counseling and/or clinical confirmation testing, and subsequently withdraw, or are withdrawn or discontinued from the study, will be replaced.

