8.2.4 Time Period and Frequency for Event Assessment and Follow-Up

Safety will be assessed by monitoring and recording potential adverse effects using the CTCAE at each study visit. Participants will be monitored by study outcome measures. If CTCAE

Page 28 of 41

grading does not exist for an adverse event, the severity of mild, moderate, severe, life-threatening, and death, corresponding to Grades 1-5, will be used whenever possible.

At each contact with the subject, the investigator will seek information on adverse events by nondirective questioning and, as appropriate, by examination. Adverse events may also be detected when they are volunteered by the subject during the screening process or between visits, or through physical examination, laboratory test, or other assessments. Information on all adverse events will be recorded in the source documentation. To the extent possible, adverse events will be recorded as a diagnosis and symptoms used to make the diagnosis recorded within the diagnosis event.

As much as possible, each adverse event or follow-up information will be evaluated to determine:

- 1. Severity grade (CTCAE Grade 1-5)
- 2. Duration (start and end dates)
- 3. Relationship to the study treatment or process [Reasonable possibility that AE is related: No (unrelated/ not suspected) or Yes (a suspected adverse reaction)]. If yes (suspected) is the event possibly, probably or definitely related to the investigational treatment?
- 4. Expectedness to study treatment or process [Unexpected if the event severity and/or frequency is not described in the investigator brochure (if applicable) or protocol].
- 5. Action taken with respect to study or investigational treatment or process (none, dose adjusted, temporarily interrupted, permanently discontinued, unknown, not applicable)
- 6. Whether medication or therapy taken (no concomitant medication/non-drug therapy, concomitant medication/non-drug therapy)
- 7. Whether the event is serious

Once an adverse event is detected, it should be followed until its resolution or until it is judged to be permanent, and assessment should be made at each visit (or more frequently, if necessary) of any changes in severity, the suspected relationship to the study treatment, the interventions required to treat it, and the outcome.

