9.2 Sample Size Determination

The difference in IES-R between groups after genetic disclosure counseling is used to determine sample size. A clinically significant difference in IES-R score is not defined. Sample size is determined from previously reported normative data of the IES-R in a community sample of N=154 non-PTSD ex-service members, demonstrating a mean of 1.82 (SD=1.05).¹⁶ A range of equivalence limits, the difference in standard deviation beyond which a significant difference would be considered relevant, are demonstrated in **Table 3** at alpha = 0.05 and power of 80%.²⁵ A sample size of N=80/counseling group (divided between PD+gene+ (45%), PD+gene- (45%), and

PD-gene+ groups (10%)), with an expected attrition of 15-20%, would allow for analysis of the primary outcome at a conservative 0.5-0.75 SD equivalence limit, and allow genetic and PD-subgroup analysis.

8		8
Equivalence limit (SD)	Per Group	Total Sample Size
0.5	80	320
0.75	36	132
1	20	80

Table 3. Sample Size Estimates.

9.3 **Populations for Analyses**

Analyses will be conducted for all randomized participants *in the* Intention-to-Treat (ITT) Analysis Dataset, as well as the Per-Protocol Analysis Dataset defined a subset of the participants in the full analysis (ITT) set who complied with the protocol sufficiently to ensure that these data would be likely to represent the effects of study intervention according to the underlying scientific model (e.g., participants who complete the 3-month study visit).

Protocol 843748-
GET VIRTUAL PD
IMAGINE-PD

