9.4 Statistical Analyses

9.4.1 General Approach

Descriptive statistics will be presented as percentages for binary variables, and as means with standard deviations or median with IQR depending on the distribution of the data. For inferential tests, the Type I error will be set at 0.05 using two-tailed tests. Covariates will be determined based on their significance as independent predictors of outcome, although age and sex will be included in all models. Check on normality will be performed through data visualization as well as using appropriate statistical tests of normality (eg Shapiro-Wilks test). Transformation of non-normally distributed continuous variables will be performed, and models will be compared to non-transformed models using non-parametric tests.

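### Section 7.2 allows withdrawal from the whole study for an adverse event with no outcome collection afterwards, so distressed participants may lose their primary IES-R score and C-SSRS follow-up

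*Combined protocol and SAP*

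**What the plan says.** Section 7.2 states that "An investigator may discontinue or withdraw a participant from the study for the following reasons" and gives a single reason: "If any clinical adverse event (AE), or other medical condition or situation occurs such that continued participation in the study would not be" in the participant's best interest. The reason is logged. Participants withdrawn after receiving counseling or confirmation testing will be replaced. The section does not say whether any outcome or safety measure is sought after withdrawal.

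Section 7.1 treats stopping the intervention differently: "Discontinuation from IMAGINE-PD or virtual/telephone genetic counseling does not mean discontinuation from the study", and the remaining procedures stay due.

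Section 8.2.4 says "Once an adverse event is detected, it should be followed until its resolution or until it is judged to be permanent", with reassessment at each visit. Section 8.2.6 has a similar rule for serious events. Neither says how this works for someone who has been withdrawn.

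The schedules in Sections 1.3 and 12.1 place IES-R and C-SSRS at Visits 3 and 4 only. (Section 8.1 also mentions a first-visit version of the C-SSRS, and 9.4.4 refers to monitoring at each visit; the schedules do not show either.) Section 9.4.2 makes the 3-month IES-R the primary outcome, analysed on available data and after multiple imputation with MICE under missing at random. No analysis under missing not at random is stated.

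**The concern.** In most trials, withdrawal for an adverse event mainly ends exposure to a treatment. Here the intervention consists of counseling on Day 0 and at disclosure. After disclosure the schedule holds only questionnaires, case report forms and adverse event review, so withdrawal at that stage mainly ends measurement.

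Section 2.3.1 names anxiety, stress, anger, sadness and guilt as the foreseeable harms, and the IES-R measures test-related distress. An adverse event that prompts withdrawal may therefore be closely related to the score that goes missing. If the more distressing disclosure mode loses more of its high scorers, the modes look more alike than they are, and in an equivalence trial that favours the hoped-for conclusion. The same participants would also leave the scheduled C-SSRS, GDS and STAI checks, although Section 2.3.3 relies on such scales to monitor safety.

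**Working it through.** **1. The plan's own figure.** Section 9.2 gives 80 per group at a 0.5 SD limit, "at alpha = 0.05 and power of 80"%. For two one-sided tests at 5% with true difference 0, n = 2 × ((1.645 + 1.282)/0.5)² = 68.5, and 68.5/0.85 = 80.6. A non-inferiority formula at one-sided 2.5% gives 2 × ((1.960 + 0.842)/0.5)² = 62.8, and 62.8/0.80 = 78.5. Either is close to 80, so the formula used cannot be identified. Section 9.4.1 says "the Type I error will be set at 0.05 using two-tailed tests" and no equivalence decision rule is written down. Two one-sided tests at 5% are therefore an assumption below, with no Bonferroni adjustment. Pooling the 1:1:1:1 factorial groups gives 160 v 160 for the disclosure comparison. With the SD of 1.05 in 9.2, 0.5 SD is 0.525 points.

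**2. What is lost, and when.** Section 12.1 has no visit between disclosure (Day 28-56) and Visit 3 (Day 90-118).

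- Withdrawal in that interval loses every scheduled IES-R and C-SSRS value. Imputation then has baseline GDS, STAI and PDQ-39 and the post-disclosure satisfaction score, but no distress score from after disclosure.
- An event first found at Visit 3 need not cost the 3-month IES-R, which is due at that visit.

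**3. Size under a common threshold (assumed).** In SD units, let the better mode have mean 0 and the worse mode mean 0.5, the limit. A participant whose distress exceeds c is withdrawn with probability q. That distress score has correlation r with the 3-month IES-R. In an arm with mean μ:

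- fraction withdrawn = q × [1 − Φ(c − μ)]
- mean of those retained = μ − r × q × φ(c − μ) / (1 − fraction withdrawn)

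Example with c = 1.5, q = 0.5, r = 1:

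- Better mode: fraction 0.5 × 0.0668 = 0.033; mean −0.5 × 0.1295/0.9666 = −0.067.
- Worse mode: fraction 0.5 × 0.1587 = 0.079; mean 0.5 − 0.5 × 0.2420/0.9207 = 0.369.
- Observed difference: 0.369 + 0.067 = 0.436, instead of 0.500.

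False-equivalence rates come from simulation at 160 v 160 (20,000 runs per row, Monte Carlo standard error at most 0.4 percentage points). With no withdrawal the rate is 5%.

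| c (SD) | q | Withdrawn, worse / better | Difference, r = 1 | False equivalence, r = 1 | Difference, r = 0.5 | False equivalence, r = 0.5 |
|---|---|---|---|---|---|---|
| 2.0 | 25% | 1.7% / 0.6% | 0.481 | 7% | 0.490 | 6% |
| 2.0 | 50% | 3.3% / 1.1% | 0.460 | 10% | 0.480 | 7% |
| 1.5 | 25% | 4.0% / 1.7% | 0.470 | 8% | 0.485 | 6% |
| 1.5 | 50% | 7.9% / 3.3% | 0.436 | 15% | 0.468 | 9% |
| 1.5 | 100% | 15.9% / 6.7% | 0.351 | 43-44% | 0.426 | 16% |

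At 80 v 80 with c = 1.5 and r = 1, the rates for q = 25%, 50% and 100% are about 7%, 11% and 27%.

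**4. Other mechanisms (160 v 160).** If each arm loses its own top 5%, the difference stays at 0.50 and the error at about 5%. If only the better arm loses its top 5%, its mean becomes −0.1031/0.95 = −0.109, the difference grows to 0.61 and false equivalence falls to 0.4%.

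**5. Replacement.** With cut-offs of 2.0 or 1.645 SD, q from 25% to 100%, r = 1 and 160 v 160, false equivalence is 7.5-35.1% without replacement and 7.7-37.8% with it. Replacing withdrawn participants does not remove the bias.

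**The case against.** The strongest reply is that the rule would seldom operate. It is discretionary and tied to best interest, and when only questionnaires remain that test would rarely be met. Distress has other routes: Section 9.4.4 sends a concerning C-SSRS to referral, Section 2.3.3 has counselors alert the investigator, and 7.1 keeps follow-up going when counseling stops. Section 2.3.3 also calls the risk of significant depression, anxiety or suicidality very low. All of this stands. It makes the loss a risk, not a certain result, and a reader who infers that the most upset participants will lose their follow-up goes beyond the text.

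Second, withdrawal must precede the 3-month IES-R, so it cannot depend on that score directly. This also stands; the r = 0.5 columns are the answer to it, and the inflation becomes smaller without disappearing.

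Third, a reader might infer that the bias always favours equivalence. Step 4 shows otherwise. A common threshold is the natural model for a judgment based on severity, but it remains an assumption.

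Fourth, a reader might take 7.2 and 8.2.4 to contradict each other. They do not: an adverse event could be followed after withdrawal. But 8.2.4 ties assessment to visits and 7.2 makes no provision for it, so the link is missing.

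What survives is that 7.2 is silent where 7.1 is explicit, on a measure that is both the harm and the endpoint.

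**Conclusion.** The point holds as a gap in data collection. Section 7.2 permits withdrawal from the whole study for an adverse event, replaces the participant and provides for no later outcomes. Between disclosure and Visit 3, this may lose the primary score and suicidality follow-up of distressed participants, and neither planned missing-data approach can recover them.

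The documents give no rate of withdrawal for adverse events, so the size is conditional. With a common threshold of 1.5 or 2 SD, 25-50% of those above it withdrawn, 160 v 160 and a true difference at the 0.5 SD limit, false equivalence rises from 5% to about 7-15% if withdrawal tracks the 3-month score, and to about 6-9% if it tracks an earlier score correlated 0.5 with it. The figure of about 43% is an upper bound for the 1.5 SD cut-off: everyone above it is withdrawn, exactly on the 3-month score. It would also assign about 16% of the worse arm to this one rule, when 9.2 expects 15-20% attrition from all causes. Equal fractions lost give no bias, and loss only in the better arm reverses the direction. The change is worth making because it is cheap and protects the primary endpoint, not because a large bias has been shown.

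**What to change.** Leave the investigator's best-interest authority as it is, and add to Section 7.2 that stopping study procedures is separate from stopping data collection:

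- After withdrawal by the investigator, the questionnaires scheduled at Visits 3 and 4 (IES-R, GDS, STAI, PDQ-39, GCOS, C-SSRS) and adverse event review are still sought, unless the participant declines them or withdraws consent.
- The date, reason and counseling mode are recorded.
- Withdrawn participants stay in the ITT set of Section 9.3 even if replaced.
- Section 7.2 is reconciled with 7.1, 8.2.4 and 8.2.6, so that it is clear how adverse events are followed after withdrawal.

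With every IES-R score kept, the simulated false-equivalence rate returns to about 5%, and the sample size does not change. The cost is a short amendment; the questionnaires are already electronic. The small downside is that some unwell participants will be sent questionnaires, which they may decline.

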7.3 Lost To Follow-Up

A participant will be considered lost to follow-up if he or she fails to return for 2 scheduled visits and is unable to be contacted by the study site staff.

The following actions must be taken if a participant fails to return to the clinic for a required study visit:

Page 24 of 41

- The site will attempt to contact the participant and reschedule the missed visit within 8 weeks and counsel the participant on the importance of maintaining the assigned visit schedule and ascertain if the participant wishes to and/or should continue in the study.
- Before a participant is deemed lost to follow-up, the investigator or designee will make every effort to regain contact with the participant (where possible, 3 telephone calls and, if necessary, a certified letter to the participant's last known mailing address or local equivalent methods). These contact attempts should be documented in the participant's medical record or study file.
- Should the participant continue to be unreachable, he or she will be considered to have withdrawn from the study with a primary reason of lost to follow-up.

	Montreal Cognitive Assessment (MoCA)	The Montreal Cognitive Assessment is a 30-point, well-validated cognitive screening tool. Cut-off values have been validated in the PD population. ²⁴

Table 2. Summary of outcome measures.

Protocol 843748-
GET VIRTUAL PD
IMAGINE-PD

8.2 Adverse Events and Serious Adverse Events

8.2.1 Definition of Adverse Events (AE)

An adverse event (AE) is any untoward medical occurrence associated with the use of an intervention in humans, whether or not considered intervention related. Intercurrent illnesses or injuries should be regarded as adverse events.

A pre-existing condition should be recorded as an adverse event if the frequency, intensity or the character of the condition changes.

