2.3 Risk/Benefit Assessment

2.3.1 Known Potential Risks

This study provides genetic counseling and testing to all participants. The method of genetic counseling varies between randomization groups. There are no known risks that differ between forms of genetic counseling including web-based, telephone, or virtual visit methods. Potential risks of genetic counseling include anxiety, stress, or discomfort that can arise during genetic counseling. Genetic counseling during this study will be conducted by trained genetic counselors following clinical guidelines genetic counseling in PD. For participants randomized to IMAGINE-PD, participants will have access to a genetic counselor via email for any follow up or clarification questions. The risks of genetic testing are relevant to all participants, which include the potential for emotional, social, or financial consequences of the testing results. Some people may feel angry, sad, anxious, or guilty about the results. There is also a risk of genetic discrimination or of re-identification of deidentified genetic results.

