8.3 Unanticipated Problems

8.3.1 Definition of Unanticipated Problems (UP)

The Office for Human Research Protections (OHRP) considers unanticipated problems involving risks to participants or others to include, in general, any incident, experience, or outcome that meets all the following criteria:

- Unexpected in terms of nature, severity, or frequency given (a) the research procedures that are described in the protocol-related documents, such as the Institutional Review Board (IRB)-approved research protocol and informed consent document; and (b) the characteristics of the participant population being studied;
- Related or possibly related to participation in the research ("possibly related" means there is a reasonable possibility that the incident, experience, or outcome may have been caused by the procedures involved in the research); and

```
Protocol 843748–
GET VIRTUAL PD
IMAGINE-PD
```

• Suggests that the research places participants or others at a greater risk of harm (including physical, psychological, economic, or social harm) than was previously known or recognized.

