8.3.2 Unanticipated Problem Reporting

Unanticipated problems (UPs) such as:

- Complaint of a participant when the complaint indicates unexpected risks, or the complaint cannot be resolved by the research team
- Breach of confidentiality
- Incarceration of a participant when the research was not previously approved under Subpart C and the investigator believes it is in the best interest of the subject to remain on the study
- Premature closure of a study (e.g., due safety, lack of efficacy, feasibility, financial reasons, etc.)

should be reported by the investigator to the Institutional Review Board (IRB). The UP report will include the following information:

- Protocol identifying information: protocol title and number, PI's name, and the IRB project number;
- A detailed description of the event, incident, experience, or outcome;
- An explanation of the basis for determining that the event, incident, experience, or outcome represents an UP;
- A description of any changes to the protocol or other corrective actions that have been taken or are proposed in response to the UP.

To satisfy the requirement for prompt reporting, UPs will be reported using the following timeline:

- UPs that are serious adverse events (SAEs) will be reported as any other SAE.
- Any other UP will be reported to the IRB within 3 months of the investigator becoming aware of the problem.

All UPs should be reported to appropriate institutional officials (as required by an institution's written reporting procedures), the supporting agency head (or designee), and the Office for Human Research Protections (OHRP) within 3 months of the IRB's receipt of the report of the problem from the investigator.

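### Social, financial and discrimination harms that section 2.3.1 names as risks of testing have no stated prospective capture and may be under-counted

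*Combined protocol and SAP*

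**What the plan says.** **Risks named.** Section 2.3.1 counts among the risks of genetic testing, for every participant, "the potential for emotional, social, or financial consequences of the testing results". It adds: "There is also a risk of genetic discrimination or of re-identification of deidentified genetic results". It gives no expected frequency or severity for any of these.

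**Adverse events.** Section 8.2.1 starts from "An adverse event (AE) is any untoward medical occurrence associated with the use of an intervention in humans", whether or not the event is thought to be related. Section 8.2.4 assesses safety with CTCAE at each visit, with a five-level fallback scale, and has the investigator ask about events without leading questions. Section 8.2.3.2 judges relatedness to genetic counseling.

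**Unanticipated problems.** Section 8.3.1 defines a UP as "any incident, experience, or outcome that meets all the following criteria". The first criterion is "Unexpected in terms of nature, severity, or frequency given" the protocol documents and the population. The second is possible relation to the research. The third is that the research carries "greater risk of harm (including physical, psychological, economic, or social harm) than was previously known or recognized". Among its reportable examples, section 8.3.2 lists a breach of confidentiality and "Complaint of a participant when the complaint indicates unexpected risks, or the complaint cannot be resolved by the research team".

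**Where records go.** Under section 10.1.5 the Safety Monitor receives safety data when an event occurs (the text prints AD or SAE, evidently meaning AE or SAE). Sections 8.2.7 and 8.3.3 tie notices to participants and consent updates to AEs, SAEs and UPs. Section 9.4.4 plans no statistical analysis of safety endpoints.

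**The concern.** Genetic testing can do harm that is not medical: a family rupture, trouble at work, a refused insurance application, a financial loss. The protocol recognises this in its risk section, but its two recording categories were written for other purposes. The AE category is medical. The UP category is for what was not foreseen, and these harms were foreseen.

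What is at stake is the completeness of the safety record. The synopsis describes the work as crucial for patient safety, and section 2.2 says the risks and benefits of these counseling methods in PD have not been evaluated. An event that fits no category would not trigger a report to the Safety Monitor, a notice to participants or a consent update. With no statistical safety analysis planned, readers would have only the raw record, and a sparse record could be taken for reassurance. Information not asked for at the follow-up visits would be hard to recover later.

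**Working it through.** The plan states no figure for these harms, so there is nothing to reproduce or recompute. The check sets the definitions side by side and follows a foreseen non-medical harm through them.

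1. **Is it an AE?** Section 8.2.1 requires a medical occurrence. Its elaborations concern illnesses, injuries and changes in pre-existing conditions. A lost job or refused policy does not fit on its own. If it leads to a medical event, such as a depressive episode, that event can be logged.

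2. **Is it a UP?** All three criteria of section 8.3.1 must hold.
   - *Foreseen in nature, severity and frequency:* it fails criterion 1, and it also fails criterion 3, because the risk is no greater than already known.
   - *Unexpected in severity or frequency alone:* it can meet criterion 1, since the three attributes are alternatives. Criterion 3 expressly admits economic and social harm, so it can be a UP.
   - *Benchmark:* section 2.3.1 names these harms by type only. Staff have no stated severity or frequency against which to judge an event unexpected, so UP status is uncertain rather than excluded.

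3. **Is it one of the listed UP examples?** Re-identification through a confidentiality breach is covered by section 8.3.2. So is a discrimination or insurance complaint that the team cannot resolve, because that limb of the example does not mention unexpectedness. Both depend on the event coming to light; neither is a question put to participants.

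4. **Does an outcome measure record it?** In Table 2 the emotional part is covered by the IES-R, GDS, STAI and C-SSRS. The GCOS is described only as measuring outcomes after counseling. The PDQ-39 is described as a health-status measure for people with PD, which leaves out the planned carriers without PD (10% × 320 = 32). No measure is described as recording social, financial or discrimination events arising from the result.

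5. **Does a scheduled procedure ask about it?** In the Schedule of Activities the only candidate row is the adverse events review at Visits 1 to 4. That row follows the definition in step 1 and the open questioning of section 8.2.4.

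**Result.** A foreseen social, financial or discrimination harm with no medical consequence, no confidentiality breach and no unresolved complaint has no stated route into the record.

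**Who is exposed.** All 320 planned participants are tested. Planned carriers are 45% + 10% = 55%, or 0.55 × 320 = 176. These figures describe exposure; they do not estimate how many events would be missed.

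**The case against.** The strongest reply is that the categories are not as closed as they look. Unexpectedness can be met by severity or frequency alone, economic and social harm is written into the UP definition, and unresolved complaints are listed as reportable. Section 8.2.4 speaks broadly of potential adverse effects, refers to the study process as well as treatment, and allows grading where CTCAE has none. The case report forms and counseling checklists are listed in section 13 but are not in the documents reviewed, so a suitable field may exist. All of this stands, and it limits the point to foreseen harms and to a risk of under-counting.

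Three stronger readings are tempting, and the documents do not support them.

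- **These harms can be recorded nowhere.** A reader might infer this from the AE and UP definitions taken together. Steps 1 to 3 of the working show several partial routes.
- **The count will be zero, and an upper confidence bound computed from it would mislead.** Open questioning could still bring such events to light and staff might record them. The protocol plans no rate, bound or claim for these harms, so a bound would answer a statement that it never makes.
- **The randomized comparison is compromised.** Section 2.3.1 attributes these harms to testing, which everyone receives, and states that no known risks differ between counseling methods. The primary objectives concern the efficacy of those methods.

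It can also be objected that widening the AE definition would be a poor remedy. AEs count whether or not they are related, so any family or money event would become reportable, and the severity wording in section 8.2.3.1 is medical. That objection is sound, and the fix below avoids it.

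**Conclusion.** The point holds as a gap in prospective data collection. The protocol names social, financial and discrimination harms as risks of testing but describes no question, instrument or category that would systematically record them when they occur in the foreseen form. They may be missed or under-counted, and may not reach the Safety Monitor.

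The size cannot be given: the documents state no expected frequency and no reporting rate. The conclusion rests on reading the AE definition literally and on the unseen case report forms having no dedicated field. If such a field exists, what remains is to state it in the protocol and say where its answers go.

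This is an inexpensive improvement to the detection of harms that the protocol itself lists. It does not touch the primary analyses.

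**What to change.** Leave the AE definition in section 8.2.1 unchanged.

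- At the AE review already scheduled at Visits 3 and 4, add one direct yes/no item, with free text, on family, employment, insurance, discrimination or financial consequences that the participant attributes to the genetic result.
- Keep the answers in a separate log and name that log in section 10.1.5 as going to the Safety Monitor. Any entry that also meets the AE or UP definition still follows that route.
- State in section 9.4.4 that counts will be reported descriptively by disclosure mode (virtual or telephone) and carrier status, which is compatible with the absence of formal safety testing.

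The cost is one extra case report form item at two existing visits, a few sentences of protocol text, and a few more entries to review.
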